## Statistical Analysis Plan for Aim 2, Hypothesis 1, 2 and 3:

- **Participant demographics:** Descriptive statistics will characterize groups. One-way ANOVA will determine differences, if any, between groups on baseline measures.
- **Behavioral Outcome measures:** A 3 group (IG, EG, BC) x 3 time (pre, post test, follow-up (1-month later)) RM ANOVA will be used to detect main effects. Appropriate post hoc tests will be used to determine within- and between-group differences,  $p<0.05$ , for **BBS, the primary outcome** measure upon which Aim 2 is powered. Statistical tests run on all secondary variables will be corrected for multiple comparisons.
- **Brain Activation Analyses for Aim 2, Hypothesis 2:** Similar to Aim 1 procedures, average percent signal change for IG and EG tasks (relative to baseline) for each participant will be extracted from the centers of gravity of the activated regions and submitted to hierarchical regression analyses to determine whether they correlate with behavioral measures (foot-tapping absolute timing errors and average amplitude). Disease severity and PD duration will be covariates. To determine the effects of time and training status we will submit the percent signal change to a 3 group (IG, EG and BC) X 2 time (pre, post) RM ANOVA. Post-hoc analyses will be corrected for multiple comparisons. The **primary outcome** will be t-contrast maps and effect size maps from ANOVA, which will be evaluated for changes in STC and CTC circuits.
- **Brain Connectivity Analyses for Aim 2, Hypothesis 3:** In Aim 2, Hypothesis 3, we will examine RSfc for increases or decreases as a function of training type and evaluate changes for correlations with improvement on behavioral outcomes. We will use regions of interest (ROIs) informed by IG and EG foot-tapping fMRI analyses in Aim 1. Seed ROIs will be 10mm spheres around centers of gravity of clusters of activation in the group level activation maps for IG and EG foot-tapping, in STC areas (posterosuperior putamen, ventral anterolateral thalamus, rostral SMA, and primary motor cortex) and CTC areas (cerebellum Larsell lobules IV, V, and VI, ventral posterolateral thalamus, primary somatosensory cortex, and the ventral premotor cortex). Seed ROIs gained from the foot-tapping task provide one path of inquiry into neural network changes that may occur after training. As RSfcMRI analyses can be extended to other important areas of brain function, we will also use behavioral measures, which may have changed (e.g., spatial

cognition) to determine other ROIs for interrogation of changes in RSfc. For all participants, we will use Pearson's correlation ( $r$ ), to correlate the time series from the seed ROIs with the time series of all other brain voxels. R-maps will undergo Fisher's  $r$  to  $z$  transformation and will be entered into a 2nd level random effects analysis for between group comparison using one way ANOVA in SPM8. T maps will be thresholded at  $p<.005$  ( $Z>2.6$ ). Correction for multiple comparisons will be carried out at cluster level according to random fields theory. Age will be a nuisance covariate in all statistical analysis. To account for head motion-related spurious differences in functional connectivity levels, a nuisance regressor based on the total amount of movement will be included in the design. To determine the effect of time and training status on each group, the  $z$  scores will be submitted to a 3 group (IG, EG, BC) x 2 time (pre, post) RM ANOVA. Post hoc analyses will be corrected for multiple comparisons. The **primary outcomes for Aim 2, Hypothesis 3** will be changes in average connectivity strength across STC and CTC circuits, as measured by average cross correlation coefficient between the seed regions of the circuits.

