This work will contribute to generalized motor theories that will impact care and create more efficient motor rehabilitation in these concrete ways: 1) This project is designed to discover general principles related to improving movement, e.g., if the IG group improves more than EG, we will assume such principles extend beyond tango and we would suggest that incorporating planning and initiating movement in mobility intervention may provide greater therapeutic effects. However, if EG improves more than IG, we would suggest cueing during training is essential for benefits. 2) Dance programs for older adults and individuals with PD are growing popular. Clinicians may use positive results from this study to suggest dance as a beneficial avenue for therapy. 3) Increased knowledge about the effects of specific types of motor training on neural circuitry will lead to greater specificity of treatment for individual patients with particular stages of disease and primary symptoms. Also, we will seek to partner with an organization, e.g., the National Parkinson Foundation to develop DVDs and manuals, presenting the training program fundamentals, graded to complexity from which clinicians can extract information relevant to their practice and incorporate as appropriate (<http://www.parkinson.org/Improving-Care/Education>.) Providing mechanistic basis for successful rehabilitative protocols involving exercise will lend greater support for clinical and community use, and may lead to insurance company support. Demonstrating mechanisms of neural circuitry will provide evidence that training may be effective in ways similar to that of pharmacology and surgical devices, e.g., DBS. This project aims to provide enjoyable treatment while investigating neural mechanisms, upon which future clinical recommendations can be made. Clearly this novel work has potential to impact care and QOL of individuals with PD.

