first we will use fMRI to investigate neural correlates of lower limb control with a foot-tapping task under IG and EG conditions in veterans with and without PD (Aim 1). Imaging studies have previously employed foot-tapping, which is used clinically to assess lower limb control. To achieve Aim 2, we will 1) evaluate the relative effectiveness of practicing IG movement (leading) versus practicing EG movement (following) versus a behavioral control (health education) for improved mobility and lower limb control, and 2) assess neural activity changes underlying improvements in lower limb control across training groups. The long-term goal is to optimize motor rehabilitative interventions for veterans with PD and understand the neural mechanisms through which the training is effective in order to further improve rehabilitation strategies for this and similar diseases.

**Specific Aim 1: Determine neural correlates of internally guided and externally guided foot-tapping in individuals with and without PD.**

**Hypothesis 1:** In healthy controls, IG and EG foot-tapping are related to task-specific neural networks of the striato-thalamo-cortical and cerebello-thalamo-cortical circuits, respectively. In those with PD relative to controls, IG foot-tapping will result in increased activation of both the STC (posterosuperior putamen, ventral anterolateral thalamus, rostral supplementary motor area, primary motor cortex) and the CTC (cerebellum (Larsell lobules IV, V, and VI), ventral posterolateral thalamus, primary somatosensory cortex, ventral premotor cortex) circuits. EG foot-tapping will result in increased activation in the CTC circuit only.

**Specific Aim 2: Determine the effect, in individuals with PD, of internally guided versus externally guided training compared to a behavioral control on: 1) mobility, and 2) whether improved mobility and foot-tapping performance after training correlate with changes in activation and resting-state functional connectivity patterns in IG and EG foot-tapping networks.**

**Hypothesis 1:** If mobility gains are related to training in planning and selecting movements, then those in IG will demonstrate greater improvements than those in EG or control. If mobility gains are related to exploiting cues during training, then those in EG will demonstrate greater improvements than those in IG or control.

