## Screening

All participants will be screened for general health with a Project Health Questionnaire. All procedures will be videotaped. We will screen for both PD-related and non-PD related impairments that could compromise the study's results. Therefore, while all outcome measures and scans will be performed in both the ON and the OFF state, mental status, sensory impairments, and depression will be *IRB 60613 Motor Training in PD*

Study Version 6/14/16

screened during optimal performance conditions: the ON state. However, we will assess disease severity in both ON and OFF states because some outcome measures could be confounded by antiparkinsonian medications. We will also assess disease severity before all outcome measure evaluations.

Mental status: We will exclude individuals with known diagnoses of dementia or vascular cognitive impairment, and screen for mental status with the Montreal Cognitive Assessment (MoCA), which has been recommended by the Parkinson Study Group. We expect to exclude some individuals who pass the MoCA yet have severe primary memory deficits, possibly because of a PD/Alzheimer's disease overlap. Therefore, we will also administer memory testing with delayed recall on the California Verbal Learning Test.

Disease Severity: A qualified and experienced rater, blinded to study purposes, will rate participants with PD for disease severity with the Movement Disorders Society Unified Parkinson Disease Rating Scale Motor Subscale III(UPDRS) in videotaped assessments. Participants must have Hoehn & Yahr staging II-III. Participants will be evaluated for disease severity with the UPDRS at the beginning of all evaluations. Participants will also complete the Freezing of Gait questionnaire, a subjective evaluation of perception of freezing of gait (FOG) in the previous week. Participants will be considered "freezers" if they answer > 1 on item 3 of the FOG questionnaire, which indicates freezing frequency of more than once per week.

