**Hypothesis 1:** Power calculations for Aim 2 are based upon an assumed 4-point improvement and effect sizes  $> 0.8$  on the BBS after 12 weeks of adapted tango, which was attained previously (see Preliminary Studies), and the minimal detectable change on the BBS in parkinsonism is 2.84 points. Therefore, with a total sample size of 63 participants (21 participants in each of 3 groups: IG, EG, and BC) a repeated measures (RM) ANOVA with 3 levels of repeat will be sensitive to between-within interaction main effect size of  $f(v) = 0.44$  ( $F_{4,114} = 2.45$ ) with a power of 0.80 at  $\alpha=.05$ . Post hoc sensitivity to effects between groups will be  $d = 0.90$ , and within groups,  $d_z = 0.65$ . To reflect an anticipated 20% attrition, we will recruit an additional 4 participants per group. Thus we will recruit 25 participants per group, for a total of 75 individuals with PD recruited for Aim 2. **Hypothesis 2:** 25 participants per group will be sufficient to detect effects for the imaging (activation and resting state) components of Aim 2 as well, based on studies conducted to determine reasonable sample sizes for fMRI studies, that demonstrate at least 20 participants in each group are necessary. **Hypothesis 3:** Differences in RSfc have been noted between different groups of individuals with PD in sample sizes of 16 per group; therefore, with 25 individuals per group, we will be able to detect differences between groups.

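### The SAP points the primary BBS analysis at main effects, but the hypothesis and the power calculation concern the group-by-time interaction; name that test, its between-group contrasts, visit and medication state

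*Combined protocol and SAP*

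**What the plan says.** - **Analysis.** The behavioral paragraph of the Statistical Analysis Plan for Aim 2 (Section 7) states: "A 3 group (IG, EG, BC) x 3 time (pre, post test, follow-up (1-month later)) RM ANOVA will be used to detect main effects". The next sentence adds: "Appropriate post hoc tests will be used to determine within- and between-group differences", at p<0.05, for BBS as primary outcome. The interaction is not named.
- **Power.** Section 7, Power Analyses for Aim 2, Hypothesis 1, says of 63 participants (21 per arm): "a repeated measures (RM) ANOVA with 3 levels of repeat will be sensitive to between-within interaction main effect size of". The size given there is f(V) = 0.44, where F on 4 and 114 df equals 2.45, power is 0.80 and alpha .05. It also gives post hoc sensitivity of d = 0.90 between groups.
- **Hypothesis.** Section 4, Specific Aim 2, Hypothesis 1: if planning and selecting movements drives the gains, "then those in IG will demonstrate greater improvements than those in EG or control"; the mirror statement follows for EG.
- **Intended conclusion.** Section 3, Significance: "if the IG group improves more than EG, we will assume such principles extend beyond tango".
- **Medication state.** Section 5, Screening: "all outcome measures and scans will be performed in both the ON and the OFF state".

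**The concern.** The plan powers one test and names others. Greater improvement in one arm than in another is a difference between arms in change over time. With the pre-training score as one of the three repeated levels, that is the group-by-time interaction. An analyst who followed the SAP literally would report a time effect and a group effect, and neither isolates the hypothesis.

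Correcting that phrase would still leave the primary result open. The plan does not say which between-group contrasts carry the conclusion, at which of the two post-training visits, or in which of the two medication states. Within-group tests stand on the same footing as between-group tests, so a significant gain within a tango arm could be presented as the primary finding without any difference from control.

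**Working it through.** **1. Which effect was powered?** Inputs: 3 groups and 3 visits, with 4 numerator df in the Aim 2 power paragraph.
- Group: 3 − 1 = 2 df
- Time: 3 − 1 = 2 df
- Group x time: (3 − 1)(3 − 1) = 4 df

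Only the interaction has 4 df.

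**2. Does the stated power reproduce for that effect?** Take noncentrality = N x f² = 63 x 0.44² = 12.2, and denominator df = (63 − 3)(3 − 1) = 120. The critical F is 2.447 and the power 0.792, against the stated 0.80. It reproduces. (The printed 114 equals 2 x (60 − 3), which belongs to N = 60, where power is 0.77. That is a separate matter and does not change which effect was powered.)

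**3. What would the named tests measure?** Let a tango arm gain 4 points, the plan's assumed improvement, and hold it, with control unchanged. Mean change from pre-training:

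| | Pre | Post | 1 month |
|---|---|---|---|
| Tango arm | 0 | 4 | 4 |
| Control | 0 | 0 | 0 |

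- Difference in change at post: (4 − 0) − (0 − 0) = 4.
- Group main effect: (0 + 4 + 4)/3 − 0 = 2.67.
- Time main effect: this averages over arms. If all three arms gained 4 points, it would be large and the interaction zero. In a simulation (21 per arm, 2,000 runs, assumed within-person correlation 0.5 to 0.8, every arm improving by 0.8 SD), the time effect was significant in all runs and the interaction in about 5%.

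**4. What else is open?**
- *Visit.* Post-test and 1 month are both in the model. The power paragraph rests on the gain after the 12-week programme, which implies the 1-week post-test but does not designate it.
- *Medication state.* Section 5, Overview, gives a reason for testing OFF, but no section designates OFF or ON for the primary BBS score.
- *Multiplicity.* Correction is promised for secondary variables and for imaging post hoc tests. None is stated for the BBS post hoc tests. Three uncorrected pairwise contrasts at 0.05 carry a family-wise error of at most 1 − 0.95³ = 0.143 if there is no true difference.

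**5. What does multiplicity control cost?** At d = 0.90 with 21 per arm (two-sided t), power is 0.81 at 0.05, which matches the stated post hoc sensitivity. At 0.05/3 = 0.0167 it is 0.66. A 2-df test of equal change across the arms, with one arm differing from the other two by d = 0.90, has f = 0.90 x √2/3 = 0.424 and power 0.845 at N = 63.

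**6. What would a baseline covariate add?** Under compound symmetry with correlation rho, a change score has variance 2·SD²(1 − rho) and the baseline-adjusted score SD²(1 − rho²). The ratio is (1 + rho)/2, that is 0.65, 0.75, 0.85 and 0.90 at rho 0.3, 0.5, 0.7 and 0.8. The documents give no rho.

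**The case against.** The strongest reply is that this is a slip which the plan itself resolves. The power paragraph says the model "will be sensitive to between-within interaction main effect size of" the stated size, so the authors use the term main effect loosely for the omnibus effect. The SAP then ties BBS to that power calculation. This reply largely stands: the authors very probably meant the interaction. It does not remove the need for a correction, because the operative sentence still says "RM ANOVA will be used to detect main effects", and fixing that phrase leaves contrasts, visit and medication state unsettled.

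Three stronger readings are tempting, and the documents do not support them.

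- *The trial loses power.* A reader might price the literal group test. With assumed SD 5, 20 per arm and both tango arms at +4, group-effect power is 0.64/0.54/0.46/0.43 at rho 0.3/0.5/0.7/0.8, against 0.59/0.76/0.95/0.99 for the interaction. The ordering reverses at rho 0.3, neither SD nor rho is in the documents, and the literal reading contradicts the power paragraph.
- *Two medication states inflate the error rate.* Two uncorrected primary tests would give up to 1 − 0.95² = 0.0975, but nowhere does the plan say that both states will be tested as primary.
- *The missing baseline covariate is a flaw.* The interaction already uses the pre-training score through change, so no bias needs repair. Under the same assumptions, a 2-df baseline-adjusted test at post has power 0.77/0.84/0.95/0.99, no material gain over the planned interaction at rho 0.7 or 0.8.

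**Conclusion.** The point holds as a specification gap that should be closed before BBS data are analysed. It rests on the degrees of freedom and the wording of the hypothesis, and needs no assumption about SD or correlation. The SAP names two 2-df effects, while the hypothesis and the powered effect are the 4-df interaction. One named effect cannot separate the arms. The other reduces a maintained 4-point advantage to 2.67 points. Loose wording is the likely cause, and the sample-size calculation for the interaction reproduces.

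The open visit and medication state are lesser gaps, since the documents hint at an answer for each without fixing it. Neither the power comparison nor the medication-state error figure supports the severity.

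**What to change.** In the behavioral outcomes paragraph of the Aim 2 analysis plan:

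1. Replace the reference to main effects with the group-by-time interaction as the primary test of BBS at alpha 0.05.
2. Base the conclusion on the between-group contrasts of change from pre-training to the 1-week post-test (IG−EG, IG−BC, EG−BC), and not on within-group change.
3. Name the multiplicity control across the three contrasts. Holm works. So does a 2-df test of equal pre-to-post change, followed by the three contrasts at 0.05 each if it is significant. The 4-df interaction alone is not a sufficient gate, because it can be significant through differences at 1 month only.
4. Make the 1-month contrasts secondary.
5. State which medication state, OFF or ON, supplies the primary BBS score, and make the other secondary. Both are already collected, and the choice is the sponsor's.

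Optional: estimate the contrasts with pre-training BBS as a covariate and no longer as an outcome level. This costs one degree of freedom and helps materially only if rho is about 0.3 to 0.5. If it becomes the primary test, restate the power sentence for it.

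The cost is SAP wording, with no new data. The stated between-group sensitivity of d = 0.90 applies to an unadjusted 0.05 test, so it should be restated for the multiplicity method chosen.

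### The primary Aim 2 comparison of Berg Balance scores never uses the pre-training score as a covariate; adding it would cut the detectable arm difference by about 5% to 13% relative to a change contrast, with no new data

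*Combined protocol and SAP*

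**What the plan says.** Section 7, Statistical Analysis Plan for Aim 2, behavioural outcomes: the BBS and the other measures go into a three-group "x 3 time (pre, post test, follow-up (1-month later)) RM ANOVA will be used to detect main effects". The arm comparisons are then left to unnamed tests: "Appropriate post hoc tests will be used to determine within- and between-group differences".

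Section 7, Power Analyses for Aim 2, Hypothesis 1: with 63 participants, 21 per group, the RM ANOVA "will be sensitive to between-within interaction main effect size of" f(V) = 0.44 at 80% power and alpha 0.05. The only figure for comparing arms follows: "Post hoc sensitivity to effects between groups will be" d = 0.90. The inputs given are a 4-point BBS improvement and effect sizes above 0.8. There is no SD and no correlation between visits.

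Baseline differences: "One-way ANOVA will determine differences, if any, between groups on baseline measures". The plan attaches no consequence to the result.

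Covariates named for Aim 2 are disease severity and PD duration (activation regressions), and age and a head-motion regressor (connectivity). Pre-training BBS is not among them. For the imaging outcome the form is the same: "we will submit the percent signal change to a 3 group (IG, EG and BC) X 2 time (pre, post) RM ANOVA".

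**The concern.** Aim 2 asks whether IG, EG and the control differ, and each arm has about 21 evaluable people. The pre-training BBS is measured on everyone and is likely to be the best single predictor of the later score. In the planned model it is treated as an outcome level. The comparison of two particular arms, which is the trial's own question, falls to tests that could use raw post scores or changes from pre, and the one stated sensitivity figure carries no baseline information.

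Two things are at stake. One is precision: part of the between-person variance that the pre score explains stays in the error term. The other is chance imbalance: in arms this small the pre-training means will differ somewhat. A raw post contrast carries part of that gap into the result, a change contrast over-corrects it, and a significance test of baseline means does neither any good.

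**Working it through.** **Inputs.** From Section 7: 21 per arm, alpha 0.05 (two-sided assumed), power 0.80, d = 0.90, dz = 0.65, f(V) = 0.44, 4 points, effect size > 0.8. Assumptions: cross-sectional SD = 4/0.8 = 5 points, an upper bound because the effect size is stated as greater than 0.8; pre-post correlation r = 0.5 to 0.8; equal variances at the two visits.

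**Step 1. The plan's own figures.** Noncentral t with 21 per arm: d = 0.90 gives power 0.812, and exactly 80% is reached at d = 0.886. With 20 per arm the corresponding values are 0.792 and 0.909. Within groups, dz = 0.65 with 21 gives 0.809. For the interaction, λ = 0.44² × 63 = 12.2 with 4 and 120 df gives 0.792. All three figures reproduce, and d = 0.90 is the value for an unadjusted two-sample t-test.

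**Step 2. Detectable difference between two arms, post versus pre.** Each contrast detects 0.90 × SD × k, with

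- raw post score: k = 1
- change from pre (the two-visit group by time contrast): k = √(2(1 − r))
- ANCOVA on the pre score: k = √(1 − r²)

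The ANCOVA-to-change variance ratio is (1 − r²)/(2(1 − r)) = (1 + r)/2.

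| r | Raw post | Change | ANCOVA | Variance ratio | Reduction, ANCOVA vs change |
|---|---|---|---|---|---|
| 0.5 | 4.50 | 4.50 | 3.90 | 0.75 | 13% |
| 0.6 | 4.50 | 4.02 | 3.60 | 0.80 | 11% |
| 0.7 | 4.50 | 3.49 | 3.21 | 0.85 | 8% |
| 0.8 | 4.50 | 2.85 | 2.70 | 0.90 | 5% |

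**Step 3. Simulation check** (21 per arm, SD 5, 6,000 runs per setting, true difference 4 points).

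| r | Raw post | Change | ANCOVA |
|---|---|---|---|
| 0.5 | 0.71 | 0.71 | 0.82 |
| 0.7 | 0.72 | 0.90 | 0.94 |
| 0.8 | 0.71 | 0.98 | 0.99 |

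Most of the advantage over raw scores at high r is already in the change contrast.

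**Step 4. If 5 is the SD of change.** The 4 points and the effect size describe improvement after training, so 5 could be the SD of the change. The change contrast then detects 0.90 × 5 = 4.5 at every r, and ANCOVA detects 4.5 × √((1 + r)/2): 3.9 at r = 0.5 and 4.3 at r = 0.8. The percentage gain is the same, 13% to 5%.

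**Step 5. Chance imbalance.** With SD 5 and 21 per arm, the standard error of the baseline gap between two arms is 5 × √(2/21) = 1.54 points, so 95% of chance gaps lie within about ±3.0 (1.96 × 1.54). For a gap of one standard error, a raw post contrast is shifted by r × 1.54 = 0.77 to 1.23 points for r = 0.5 to 0.8. A change contrast is shifted the other way by (1 − r) × 1.54 = 0.77 to 0.31. ANCOVA removes the expected shift.

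**The case against.** The strongest reply is that the planned model does use the pre score. The powered test is the group by time interaction, and that compares changes. This stands. A reader might infer from d = 0.90 and an SD of 5 that the trial can detect only 4.5 points where ANCOVA would detect 2.7. The documents do not support that. The 4.5 is a raw post-score figure. It is also the change-contrast figure at r = 0.5, but at r = 0.8 the change contrast already reaches 2.85. The raw figure would apply only if the unnamed post hoc tests compare raw post scores, which the plan neither says nor excludes.

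A reader might also take the words about main effects to mean a group main effect averaged over all three visits, which would be weaker still. With equal correlations and an effect at both later visits, it detects 0.90 × 5 × √((1 + 2r)/3) × 3/2, or 5.5 to 6.3 points for r = 0.5 to 0.8. But the power section rests on the interaction, so that reading is not the natural one.

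Nor is the planned analysis biased. A group by time RM ANOVA is standard and unbiased over randomisation; the over-correction in Step 5 is conditional on an observed chance gap. The precision advantage also shrinks as r approaches 1.

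Three limits remain. SD and r are not in the documents. The gain for imaging outcomes has not been quantified. And Section 5 admits only those who complete all 20 lessons to the analysis, so these calculations describe completers, and a covariate does not repair selection after randomisation. None of these removes the gain or adds to its cost.

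**Conclusion.** The point holds as an inexpensive improvement in precision. No Aim 2 analysis adjusts for pre-training BBS, and the arm contrast that answers the trial's question is not named. Against the change contrast, a baseline covariate makes the detectable difference 13% smaller at r = 0.5, falling to 5% at r = 0.8. In points this is 4.5 to 3.9 and 2.85 to 2.7, if the cross-sectional SD is 5. If 5 is the SD of change, the ANCOVA figures are 3.9 to 4.3 against 4.5. A smaller SD scales every figure down in proportion. The gain is larger only if the post hoc tests would have used raw post scores: 4.5 against 3.9 to 2.7 with a cross-sectional SD of 5.

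**What to change.** In Section 7, Statistical Analysis Plan for Aim 2:

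- Name a baseline-adjusted contrast as the primary between-arm BBS analysis: an ANCOVA, or a model of post and follow-up with pre-training BBS as a covariate. Participants are tested OFF and ON medication, so take the covariate from the same state as the outcome.
- Report adjusted IG–EG, IG–BC and EG–BC differences with 95% CIs.
- Do not rely on the baseline one-way ANOVA to deal with imbalance; describe baseline values instead.
- The same form can serve the secondary outcomes and the region-level imaging summaries (percent signal change, average connectivity), without a claimed size of gain.

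In Power Analyses for Aim 2, state the sensitivity of the adjusted contrast as about 0.90 × √(1 − r²) for a stated range of r. That is 0.78 at r = 0.5 and 0.54 at r = 0.8. State also the SD assumed, and whether it is the SD of scores or of change.

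The cost is SAP wording and one error degree of freedom. The pre-training score is already collected.
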